#### **2.5.5 Unscheduled visits**

Unscheduled visit measurements of laboratory data, vital signs, and ECG will not be included in the by-visit summaries (unless it is for repeat liver or spleen volume assessment), but will be used for computation of baseline and/or worst values.

#### **2.5.6 Pooling of centers for statistical analyses**

None planned.

#### **2.5.7 Statistical technical issues**

Not applicable.

### 3 INTERIM ANALYSIS

There is no interim analysis planned. However, early analysis, including major efficacy and safety endpoints, will be performed after the last patient enrolled and completed 2 years of treatment (two-year analysis period).

Only data collected up to the date of all patients completed 2-year analysis period will be used for this early analysis.

Summary of patient disposition, demographics and key baseline characteristics, prior and concomitant medications, extent of IMP exposure and compliance will be provided, as described in [Section 2.2](#), [Section 2.4.1](#), [Section 2.4.2](#), and [Section 2.4.3](#), respectively, in the analysis report.

For efficacy endpoints, the 2-year analysis will be performed for the following efficacy endpoints in which details are provided in [Section 2.4.4](#).

- Mobility, bone pain and bone crisis, as assessed by the Gaucher Disease clinical assessments
- Bone marrow infiltration
- BMD
- Lytic lesions, osteonecrosis, fractures and infarcts
- Bone biomarkers
- Blood levels of biomarkers of GD1 (chitotriosidase, plasma GL-1 and lyso-GL-1)
- Gaucher disease related hematology assessment (hemoglobin, platelet)
- Spleen volume and liver volume

For safety endpoints, key safety results including TEAE, SAE, AESI, death, AEs leading to treatment discontinuation along with related laboratory values, in which details are provided in [Section 2.4.5](#) will be provided in the 2-year analysis report.

## 4 DATABASE LOCK

The 2-year analysis is planned to be locked approximately 28 days after last patient completed 2-year follow-up. The final database is planned to be locked at approximately 28 days after last patient last visit.

## 5 SOFTWARE DOCUMENTATION

All tables, listings, and figures will be generated in a validated environment using SAS® version 9 or higher.

## Appendix A SF-36 health survey

A number of computations must be carried out to go from SF-36 questionnaire responses to summary scores. These computations are described in this section.

Each questionnaire item has a final item value, which will be used in the computation of the raw score for each of the eight scales. Many questionnaire items have a final item value that is equivalent to its pre-coded item value. Prior to any summary scores being calculated, ten items in the questionnaire will be re-coded according to the developer's instructions as follows:

Item 7

Response Choices	Pre-coded Item Value	Final Item Value
None	1	6.0
Very Mild	2	5.4
Mild	3	4.2
Moderate	4	3.1
Severe	5	2.2
Very Severe	6	1.0

Item 8 – if both Items 7 and 8 are answered.

Response Choices	Item 8 Pre-coded Item Value	Item 7 Pre-coded Item Value	Final Item Value
Not At All	1	1	6
Not At All	1	2 through 6	5
A Little Bit	2	1 through 6	4
Moderately	3	1 through 6	3
Quite A Bit	4	1 through 6	2
Extremely	5	1 through 6	1

Item 8 – if Item 7 is not answered.

Response Choices	Pre-coded Item Value	Final Item Value
Not At All	1	6.0
A Little Bit	2	4.75
Moderately	3	3.5
Quite A Bit	4	2.25
Extremely	5	1.0

Item 1

Response Choices	Pre-coded Item Value	Final Item Value
Excellent	1	5.0
Very Good	2	4.4
Good	3	3.4
Fair	4	2.0
Poor	5	1.0

Items 11b and 11d

Response Choices	Pre-coded Item Value	Final Item Value
Definitely True	1	5
Mostly True	2	4
Don't Know	3	3
Mostly False	4	2
Definitely False	5	1

Items 9a, 9d, 9e and 9h

Response Choices	Pre-coded Item Value	Final Item Value
All of the Time	1	5
Most of the Time	2	4
Some of the Time	3	3
A Little of the Time	4	2
None of the Time	5	1

Item 6

Response Choices	Pre-coded Item Value	Final Item Value
Not At All	1	5
Slightly	2	4
Moderately	3	3
Quite A Bit	4	2
Extremely	5	1

Item 2

Response Choices	Pre-coded Item Value	Final Item Value
Much Better	1	5
Somewhat Better	2	4
About the Same	3	3
Somewhat worse	4	2
Much worse	5	1

Raw scale scores are calculated using final item values. The raw scale scores will be computed by taking the sum of the items for that particular scale (see Table below). A respondent has to have answered at least 50% of the items contributing to a particular scale for a raw scale score to be computed. If the respondent did not answer at least 50% of the items contributing to a particular scale at a particular time point, the raw scale score will be set to missing for that scale for that respondent for that particular time point. If a respondent has answered at least 50% of the items contributing to a particular scale but some of the items were not answered, the missing items will be estimated by the average score across the items that were answered.

Each raw scale score will then be transformed to a 0 to 100 scale using the following formula:

$$\text{Transformed Scale} = \frac{[\text{Actual raw score} - \text{Lowest possible raw score}]}{\text{Possible raw score range}} \times 100$$

Lowest possible raw score and possible raw score range values are:

SF-36 Raw and Transformed Scale Score Specifications			
Scale	Sum of Final Item Values for Raw Scale Score	Lowest And Highest Possible Raw Scores	Possible Raw Score Range
Physical Functioning (PF)	3a + 3b + 3c + 3d + 3e + 3f + 3g + 3h + 3i + 3j	10, 30	20
Role-Physical (RP)	4a + 4b + 4c + 4d	4, 20	16
Bodily Pain (BP)	7 + 8	2, 12	10
General Health (GH)	1 + 11a + 11b + 11c + 11d	5, 25	20
Vitality (VT)	9a + 9e + 9g + 9i	4, 20	16
Social Functioning (SF)	6 + 10	2, 10	8
Role-Emotional (RE)	5a + 5b + 5c	3, 15	12
Mental Health (MH)	9b + 9c + 9d + 9f + 9h	5, 25	20

The two overall summary scores will be calculated by first determining the Z-scores for the eight scales as follows:

$$Z - \text{score} = \frac{(\text{raw scale score} - \text{mean})}{SD}$$

where mean and SD are the appropriate mean and standard deviation of the 1998 general U.S. population (1). Z-scores are in standard deviation units.

The raw PCS and MCS summary scores will be computed by multiplying the z scores for the raw component scores (PCS: PF, RP, BP, GH, VT, SF, RE, MH; MCS: PF, RP, BP, GH, VT, SF, RE, MH) by the corresponding scoring coefficients (from the general U.S. population [1]) and taking the sum of those values. Finally, the PCS and MCS will be standardized as follows:

$$\text{PCS} = (\text{raw PCS} \times 10) + 50$$

$$\text{MCS} = (\text{raw MCS} \times 10) + 50$$

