### **2.4.7 Analyses of quality of life/health economics variables**

The score for each scale will be estimated from the Short Form-36 Health survey [SF-36]. The overall physical component scale (PCS) and mental component scale (MCS) will be computed. Summary statistics as well as change and percentage change from baseline (study and eliglustat) by visit by all SF-36 QOL variables will be presented.

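### SAP Appendix A builds the SF-36 Z-scores from raw item sums without stating the metric of the norms; if the norms are on 0–100, PCS and MCS come out wrong

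*SAP*

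**What the plan says.** SAP Appendix A sets out the SF-36 scoring in four steps.

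1. Item sums: "The raw scale scores will be computed by taking the sum of the items for that particular scale". A table gives the limits, from 10–30 for physical functioning (PF) down to 2–10 for social functioning (SF).
2. Rescaling: "Each raw scale score will then be transformed to a 0 to 100 scale using the following formula".
3. Z-scores: the sentence "The two overall summary scores will be calculated by first determining the Z-scores for the eight scales as follows" introduces a formula whose numerator is the raw scale score minus a mean, divided by an SD. The source of both is described so: "where mean and SD are the appropriate mean and standard deviation of the 1998 general U.S. population". A manual is cited. No mean or SD is printed, and no unit is stated.
4. Summary scores: PCS and MCS are obtained by "multiplying the z scores for the raw component scores" by scoring coefficients and summing. The result is multiplied by 10 and 50 is added. The coefficients are not printed either.

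SAP Section 2.4.7 says "The overall physical component scale (PCS) and mental component scale (MCS) will be computed" and asks for summary statistics, change and percent change by visit from both study baseline and eliglustat baseline. Protocol Section 11.4.5 leaves the SF-36 derivation to the SAP, so Appendix A is the operative specification.

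**The concern.** A Z-score is meaningful only if the score, the mean and the SD are in the same units. Appendix A creates two versions of each scale score, gives them different names, and takes the raw one into the Z formula. The sentence on the summary scores again speaks of raw scores, so a single slip in the formula is a weak explanation. No sentence carries the 0–100 score into PCS or MCS.

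A programmer following the text enters the item sum and has to work out which metric the norms are on. If they are on 0–100, PCS and MCS levels, changes and percent changes are all distorted, and the eight scales no longer carry the relative weights that the coefficients intend. Protocol Section 9.5.1 expects these patients to be stable, so a shrunken change would not look odd. If a feeder study's PCS and MCS had been scored on another metric, the change from eliglustat baseline would partly reflect the scoring.

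**Working it through.** **Inputs.** Lowest score, highest score and range for each scale come from the Appendix A table. The norm means and SDs are not in the documents, so they are assumed below and varied: means of 50 to 85 and SDs of 15 to 30 on 0–100.

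**The plan's own figures.** Each range should equal the number of items × (highest − lowest item value). PF: 10 × (3 − 1) = 20. RP and VT: 4 × (5 − 1) = 16. BP: 2 × (6 − 1) = 10. GH and MH: 5 × (5 − 1) = 20. SF: 2 × (5 − 1) = 8. RE: 3 × (5 − 1) = 12. All eight agree with the table.

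**Case 1: norms in raw-sum units.** Let T = (raw − lowest)/range × 100. A 0–100 norm mean m and SD s correspond in raw units to lowest + m × range/100 and s × range/100. Then (raw − raw mean)/(raw SD) = (T − m)/s. The formula as written is exact. A numerical check over all scales and the assumed norms gave a largest difference of about 1e-15, which is rounding error.

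**Case 2: norms on 0–100 (assumption).** A change of d points in T is a change of d × range/100 in the raw score. The formula as written gives a change in Z of d × range/(100 × s); the correct change is d/s. The understatement is therefore 100/range and does not depend on the mean or SD. The last column takes d = 10 and an assumed SD of 20, for which the correct change is 10/20 = 0.50 on every scale.

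| Scale | Range | Understatement (100/range) | Change in Z as written |
|---|---|---|---|
| PF, GH, MH | 20 | 5 | 0.10 |
| RP, VT | 16 | 6.25 | 0.08 |
| RE | 12 | 8.33 | 0.06 |
| BP | 10 | 10 | 0.05 |
| SF | 8 | 12.5 | 0.04 |

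The retained fraction runs from 0.20 (PF, GH, MH) to 0.08 (SF), and 0.20/0.08 = 2.5. The relative weight of the scales within PCS and MCS would therefore shift by up to 2.5-fold.

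**Levels in case 2.** A patient exactly at the norm should have Z = 0. The extremes over the assumed range are:
- PF, mean 50, SD 30: raw = 10 + 50 × 20/100 = 20, so Z = (20 − 50)/30 = −1.00.
- SF, mean 85, SD 15: raw = 2 + 85 × 8/100 = 8.8, so Z = (8.8 − 85)/15 = −5.08.

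The highest raw score on any scale is 30. Any norm mean above 30 therefore gives a negative Z even at the best possible score. With an assumed mean of 70 and SD of 20, a perfect PF score gives (30 − 70)/20 = −2.00, where the correct value is (100 − 70)/20 = 1.50.

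**What cannot be computed.** The resulting error in PCS and MCS themselves, because the coefficients are not in the documents.

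**The case against.** The strongest reply is that the SAP asks for the appropriate mean and SD, which can fairly be read as norms matched to the score in the formula. With raw-unit norms nothing is wrong, and the documents do not rule that out. This stands, and it makes the size of the error conditional. It does not settle the matter, because the text never says what the norms must match.

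A reader might infer that PCS and MCS will certainly be wrong. The documents do not support that: they give neither the values nor the units of the norms, and no figure printed in Appendix A is miscalculated. The 5- to 12.5-fold factors are per-scale ratios under one assumption, not errors in PCS or MCS.

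A reader might also infer that the 0–100 scores serve no purpose, or that a real change in quality of life would go unseen. Neither follows. SAP Sections 2.1.6 and 2.4.7 report the eight scales in their own right, and a real change would still appear there.

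The reach is also limited, and this stands in full. Nothing is tested. Quality of life is a secondary objective. SF-36 appears neither among the two-year efficacy endpoints listed in SAP Section 3 nor in the endpoint tables of Appendix B. Finally, SAP Section 2.4 already makes eliglustat baseline depend on comparable assessments, including result evaluation. That is a general condition, and it does not say how SF-36 is to be scored.

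**Conclusion.** The point holds in conditional form. Appendix A enters the raw item sum in the Z formula straight after rescaling it to 0–100, and leaves the metric of the norms unstated. With 0–100 norms, changes in Z are understated 5- to 12.5-fold, unequally across scales. Levels fall below the norm on any scale whose norm mean exceeds 30, and the eight scales are reweighted within PCS and MCS. With raw-unit norms the error is zero. The documents do not show which case applies.

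Only PCS and MCS are affected. The eight 0–100 scale scores, the primary skeletal endpoints and the safety results do not depend on this step. The correction is still worth making, because this is an explicit scoring rule that gives wrong summary scores under one open reading, and a rule that is right under both readings costs almost nothing.

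**What to change.** In Appendix A, replace the raw scale score in the Z formula with the transformed 0–100 scale score, and make the same replacement where the summary-score sentence refers to raw component scores. The terms raw PCS and raw MCS, meaning the sums before standardisation, can stay.

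State that the norm mean and SD are on the 0–100 metric. If the source gives them in raw units, convert them: mean = (raw mean − lowest)/range × 100, and SD = raw SD/range × 100. Z is then correct whichever form the source uses.

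State that feeder-study SF-36 data used for eliglustat baseline are scored by the same rule. Printing the eight means and SDs and the PCS and MCS coefficients would make the scores reproducible from the SAP alone, but this is optional.

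The cost is a short SAP correction, with no new data and no change to any other endpoint. It is best made before PCS and MCS outputs are seen, so that it is not a post hoc change of scoring.

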## Appendix B Summary of statistical analyses

### EFFICACY ANALYSIS

Endpoint	Analysis population	Primary analysis	Supportive analysis	Subgroup analysis	Other analyses
Primary endpoints					
Gaucher Disease clinical assessments: Mobility, bone pain, bone crisis	FAS	Descriptive statistics	No	No	No
Bone marrow infiltration	FAS	Descriptive statistics	No	No	No
Bone mineral density (BMD)	FAS	Descriptive statistics	No	No	No
Lytic lesions, osteonecrosis, fractures and infarcts	FAS	Descriptive statistics	Annual incidence rate	No	No
Bone biomarker	FAS	Descriptive statistics	No	No	No
Secondary endpoints					
GD-1 biomarker	FAS	Descriptive statistics	No	No	No

### SAFETY ANALYSES

Endpoint	Analysis population	Primary analysis	Supportive analysis	Subgroup analysis	Other analyses
Adverse events	Safety	Descriptive statistics	No	No	No
Laboratory, other safety	Safety	Descriptive statistics	No	No	No

Signature Page for VV-CLIN-0541888 v2.0  
efc13781-16-1-9-sap

Approve & eSign

[REDACTED]

[REDACTED]

Approve & eSign

[REDACTED]

Clinical

[REDACTED]
